00-06	02.04.25	All chapters	Further adaptions based on discussion of [name] and [name]; Review of mediation analysis by [name]
00-07	29.04.25	All chapters	Further adaptions based on comments of [name] (15.04.)
01	04.06.25	All chapters	Minor changes before finalisation

Version 1.0 Page 3 of 18

Abbreviations

Abbreviation	Definition
ACE-D	Adverse Childhood Experience Questionnaire German version
AE	Adverse event
B-IPQ	Brief Illness Perception Questionnaire
CFS	Chalder Fatigue Scale
CI	Confidence interval
CMA	Causual mediation analysis
CONSORT	Consolidated Standards of Reporting Trials
COV.EXPECT	Expectation management intervention
COV.SUPPORT	Supportive intervention
CSQ-CAT	Coping Strategies Questionnaire-Catastrophizing Subscale
DSM-5	Diagnostic and Statistical Manual of Mental Disorders, Fifth Edition
DSQ-PEM	DePaul Symptom Questionnaire Post-Exertional Malaise
EFS	Evaluated for Safety Set
ERQ	Emotion Regulation Questionnaire
EURONET SOMA	European Network to improve diagnostic, treatment and health care for patients
	with persistent somatic symptoms)
FAS	Full Analysis Set
FIML	Full information maximum likelihood
GAD-7	Generalized Anxiety Disorder-7
IEC	Independent ethics committee
IRB	Institutional review board
ITT	Intention-To-Treat
MAR	Missing at random
NRS	Numeric Rating Scale
PD	Protocol deviation
PDI	Pain Disability Index
PHQ-15	Patient Health Questionnaire 15
PHQ-15	PAIS Patient Health Questionnaire-15 Post-Acute Infection Syndromes
PHQ-9	Patient Health Questionnaire-9
PM	Percentage mediated
PP	Per Protocol
PSS-10	Perceived Stress Scale-10
REDCap	Research Electronic Data Capture
SAE	Serious adverse event
SAP	Statistical Analysis Plan
SCID	Structured Clinical Interview for the DSM-5
SCQ-D	Self-Administered Comorbidity Questionnaire
SSAS S	omatosensory Amplification Scale
SSD-12	Somatic Symptom Disorder – B Criteria Scale
TAS-20	Toronto Alexithymia Scale-20
TAU	Treatment as usual
TEX-Q	Treatment Expectation Questionnaire
WI-7	Whiteley-Index-7

Version 1.0 Page 4 of 18

Content

IMBE

1	In	troductio	n	7
	1.1	Backgr	ound and Rationale	7
	1.2	Study (Objectives	7
	1.3	Study I	Endpoint(s)	7
2	St	udy Meth	ods	9
	2.1	Trial D	esign	9
	2.2	Randomisation		9
	2.3	Sample Size		9
	2.4	Statist	ical Interim Analyses and Stopping Guidance	9
	2.5	Timing	of Analyses	9
3	St	atistical P	rinciples	10
	3.1	Confid	ence Intervals and P Values	10
	3.2	Adhere	ence and Protocol Deviations	10
	3.3	Analys	is Populations	10
		3.3.1	Full Analysis Set (FAS)	10

1.1 Background and Rationale

After an infection with the severe acute respiratory syndrome coronavirus type 2 (SARS-CoV-2) has abated, a substantial portion of affected patients do not fully recover, but suffer from persistent somatic symptoms - a phenomenon often described as "Long COVID". There is growing evidence that the development of Long COVID is multifactorial and involves pathophysiological, psychological, and social mechanisms. Among psychological risk factors, particularly increased levels of illness-related anxiety and dysfunctional symptom expectations appear to contribute to processes of symptom persistence after COVID-19.

1.2 Study Objectives

With regard to the development of effective therapies, our primary aim is to investigate whether symptoms of Long COVID can be improved by a targeted modification of illness-related anxiety and dysfunctional symptom expectations. Second, we aim to prospectively identify further risk factors that contribute to the persistence of Long COVID, and compare them with risk factors for somatic symptom persistence in other medical conditions.

Hypothesis 1: The therapeutic modification of illness-related anxiety and dysfunctional symptom expectations improves Long COVID symptom severity.

Hypothesis 2 (exploratory): In addition to illness-related anxiety and dysfunctional symptom expectations, further risk factors contributing to the persistence of Long COVID symptoms can be identified.

Hypothesis 3 (exploratory, using results of SOMACROSS): Long COVID and other medical conditions share common risk factors for somatic symptom persistence.

1.3 Study Endpoint(s)

Primary endpoint:

 Change from baseline in overall somatic symptom severity at 3 months measured with the sum score of the Patient Health Questionnaire 15 (PHQ-15)

Secondary endpoints:

- Change from baseline in overall somatic symptom severity at 6 weeks and 6 months measured with the PHQ-15
- Subjective improvement of Long COVID symptoms (improved vs. stable / worsened) at 6 weeks, 3 months, and 6 months
- Change from baseline in fatigue measured with the Chalder Fatigue Scale (CFS) at 6 weeks, 3 months, and 6 months
- Change from baseline in pain measured with an adapted version of the Pain Disability Index (PDI) at 6 weeks, 3 months, and 6 months

Version 1.0 Page 7 of 18

- Post-exertional malaise measured with the DePaul Symptom Questionnaire Post-Exertional Malaise (DSQ-PEM) at 6 weeks, 3 months, and 6 months
- Change from baseline in long COVID symptoms measured with the Patient Health Questionnaire-15 Post-Acute Infection Syndromes (PHQ-15 PAIS) at 6 weeks, 3 months, and 6 months
- Somatic symptom disorder evaluated with the Structured Clinical Interview for the Diagnostic and Statistical Manual of Mental Disorders, Fifth Edition (DSM-5) (SCID-5) at 3 months
- Change from baseline in symptom perception measured with the Brief Illness Perception Questionnaire (B-IPQ) at 3 months and 6 months

Mediator variables (all variables are measured at BL, 6 weeks, 3 and 6 months):

- Illness-related anxiety measured with the Somatic Symptom Disorder B Criteria Scale (SSD-12)
- Treatment expectations measured with the Treatment Expectation Questionnaire (TEX-Q)
- Expectation of symptom severity, of symptom burden, and of coping with symptoms measured with the European Network to improve diagnostic, treatment and health care for patients with persistent somatic symptoms (EURONET SOMA) Numeric Rating Scales (NRS)

Version 1.0 Page 8 of 18

2 Study Methods

In this chapter, a summary of the basic study methods is provided.

2.1 Trial Design

The SOMA.COV trial is a monocentric, nationwide, prospective, observer-blinded, three-arm parallel randomised controlled trial in patients \geq 18 years after SARS-CoV-2 infection with Long COVID and at least moderately severe ongoing symptoms (PHQ-15 \geq 10). Eligible patients that gave informed consent are randomised in one of the two experimental arms or to the control arm with an allocation ratio of 1:1:1. In the control group patients receive treatment as usual (TAU) only. Patients randomised to one of the experimental groups receive either a supportive intervention (COV.SUPPORT) or an expectation management intervention (COV.EXPECT), both additional to TAU.

This study is associated with the SOMACROSS research unit (FOR 5211), funded by the German Research Foundation (Deutsche Forschungsgemeinschaft, DFG) which investigates mechanisms of somatic symptom persistence across different medical conditions. (Löwe et al., 2022)

2.2 Randomisation

Patients are randomised to COV.EXPECT, COV.SUPPORT or TAU with an allocation ratio of 1:1:1. The randomisation is stratified by sex with a block randomisation procedure with varying block length. The randomisation list was generated using R software (R Project for Statistical Computing) by an independent member of the biostatistics unit and uploaded in REDCap (Research Electronic Data Capture), a software for building and managing online surveys and databases.

The randomisation is performed directly after verification that no inclusion criteria are violated and no exclusion criteria are met. Baseline data are collected afterwards.

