3.2 Adherence and Protocol Deviations

Both experimental arms (COV.EXPECT, COV.SUPPORT) receive three individual online video consultation sessions with an interval of 2 weeks with given homework after each session and a booster session after 3 months, each lasting 45 minutes. The adherence to the intervention is evaluated based on the number and duration of attended online sessions.

Major protocol deviations will lead to exclusion of a subject from the Per Protocol Population (see Section 3.3.2). Major protocol deviations are any unapproved changes in the research study design and/or procedures that are within the investigator's control and not in accordance with the independent ethics committee (IEC) / institutional review board (IRB) - approved protocol that may affect the subject's rights, safety or well-being, or the completeness, accuracy and reliability of the study data.

Protocol deviations (PD) are defined as follows:

Major PDs:

- Violation of in- and exclusion criteria
- PHQ-15 < 10 in the baseline assessment (in deviation from the inclusion screening)
- At 3-month follow-up:
 - More than 1 missing intervention session (COV.EXPECT, COV.SUPPORT)
 - More than 1 substantially shortened intervention session (< 30 minutes session time)

Additionally, there will be a blind review of a list of further detected protocol violations. The principal investigator will decide which reported protocol violations are considered major and potentially impact the study results.

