5.3 Efficacy Evaluation

5.3.1 Analysis of Primary Endpoint(s)

The analysis of the primary endpoint is based on the FAS and thus is as close as possible to the ITT principle.

The primary outcome is analysed with a linear mixed effects model with the change from baseline of the PHQ-15 score at 6 weeks and 3 months as dependent variable, treatment group (COV.EXPECT, COV.SUPPORT, and TAU), time (categorical: 6 weeks and 3 months), the stratification variable gender as well as baseline PHQ-15 as fixed effects and patient as random effect. Further, the interaction between time and random group is included and will be excluded from the model if the test result of the interaction is p≥0.05. If the interaction remains in the model, the respective contrast at 3 months will be explored further. If it is removed from the model, the overall treatment effect remains stable over time and can also be interpreted as the effect at the interesting time point 3 months.

The estimation will be performed using Maximum-Likelihood estimation with an AR(1)-structure for residual errors.

For the primary hypothesis, the global treatment effect will be tested first using the F-Test (two-sided). If the p-value is < 0.05, the contrasts in change for COV.EXPECT vs. TAU and COV.SUPPORT vs. TAU at a 5% level (two-sided) will be tested using the Wald test. Because of the closed testing principle an adjustment of the contrast p-values for multiplicity is not necessary. Mean difference estimates together with 95% confidence intervals will be reported.

After final database closure this analysis is repeated with an analogous model that further includes the measurement of the 6 months follow-up. The 3-months estimates from this model will only be interpreted as sensitivity analyses of the primary endpoint analysis.

The assumptions regarding normality of residuals are examined graphically. Histograms and quantile-quantile plots are used to evaluate normality of residuals. In case of unmet assumptions data can be transformed accordingly.

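### Baseline PHQ-15 is taken after randomisation and anchors the primary model: prespecify a sensitivity analysis on the screening PHQ-15, cover patients with no baseline, and state when allocation was disclosed

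*SAP*

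**What the plan says.** On the order of events, SAP section 2.2 is explicit: "The randomisation is performed directly after verification that no inclusion criteria are violated and no exclusion criteria are met". It then adds: "Baseline data are collected afterwards".

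On blinding, section 2.1 describes a "monocentric, nationwide, prospective, observer-blinded, three-arm parallel randomised controlled trial". It does not claim that patients are blinded, and the control condition is easy to recognise: "In the control group patients receive treatment as usual (TAU) only".

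The baseline PHQ-15 is used in three places:

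- Primary endpoint (section 1.3): "Change from baseline in overall somatic symptom severity at 3 months measured with the sum score of the Patient Health Questionnaire 15 (PHQ-15".
- Primary model (section 5.3.1), which includes "the stratification variable gender as well as baseline PHQ-15 as fixed effects".
- Major protocol deviations (section 3.2), which include "PHQ-15 < 10 in the baseline assessment (in deviation from the inclusion screening").

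The last item shows that a separate PHQ-15 was taken at screening. Section 2.1 makes a score of at least 10 an entry condition, so that value precedes randomisation. No efficacy model in the SAP uses it. The SAP does not say when patients learn their allocation.

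**The concern.** A baseline covariate is harmless to a randomised comparison because allocation cannot have influenced it. A questionnaire completed after randomisation, by patients who may know their arm, lacks that guarantee. This trial's own hypothesis is that illness anxiety and symptom expectations drive symptom severity, so news of allocation could plausibly colour the next symptom rating. If it does, adjusting for that rating carries part of the reaction into the treatment estimate.

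Two further consequences do not depend on when allocation was disclosed:

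- A randomised patient who never completes the baseline questionnaire has neither a change score nor a covariate value, and so leaves the primary model. Section 3.3.1 describes the full analysis set as close to all randomised patients.
- The per-protocol set selects patients on a value measured after randomisation.

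**Working it through.** **Plan's own figure.** For d = 0.5, two-sided alpha 5% and power 80%, the two-sample t-test needs 63.8, so 64 per group (power 80.1%). With 25% loss, 64 / 0.75 = 85.3, so 86 per arm, and 3 × 86 = 258. Section 2.3 reproduces and is not in dispute.

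**Assumptions.** The SAP gives neither of these, so both are assumed:

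- r, the slope of follow-up on baseline PHQ-15 (scores in SD units): 0.5 to 0.7.
- s, the shift in reported baseline between COV.EXPECT and TAU caused by knowing the allocation: 0.2 SD as the central case, 0.1 to 0.3 SD as the range.

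**Bias.** With baseline in the model, analysing the change or the follow-up score gives the same treatment estimate. There is one route, not two:

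bias = −r × s

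- s = 0.2: 0.5 × 0.2 = 0.10 SD; 0.6 × 0.2 = 0.12 SD; 0.7 × 0.2 = 0.14 SD.
- Full range: 0.5 × 0.1 = 0.05 SD to 0.7 × 0.3 = 0.21 SD.

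Against d = 0.5 in raw-score SDs, the s = 0.2 bias is 20 to 28% of the planned effect. If d is in change-score SDs, d corresponds to 0.5 × √(2 − 2r) raw SDs, and the share is 20 to 36%.

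**Direction.** Higher PHQ-15 means more severe symptoms. If COV.EXPECT patients report higher baselines than TAU patients, the benefit is overstated. If TAU patients report higher baselines, it is understated.

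**False-positive rate, contrast alone.** SE = √(2(1 − r²)/64), 64 per arm, no true effect, s = 0.2:

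| r | bias | SE | bias/SE | two-sided error |
|---|---|---|---|---|
| 0.5 | 0.10 | 0.153 | 0.65 | 10.0% |
| 0.6 | 0.12 | 0.141 | 0.85 | 13.6% |
| 0.7 | 0.14 | 0.126 | 1.11 | 19.8% |

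A two-arm simulation at r = 0.6 (20,000 runs) gave a bias of 0.119 SD and an error of 13.4%.

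**False-positive rate under the planned procedure.** Section 5.3.1 tests the contrast only if the global F-test gives p < 0.05. I simulated three arms of 64 with a single-visit baseline-adjusted model (20,000 runs per setting). Requiring both tests to be significant gave about 6%, 8% and 13% for r = 0.5, 0.6 and 0.7. With no shift it gave about 2.5%. The results were much the same whether the shift was in COV.EXPECT only, in both active arms or in TAU. When TAU was shifted upwards, almost all false positives pointed to harm; false claims of benefit stayed below 0.3%.

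**Missing baseline.** The outcome is follow-up minus baseline, and baseline is also a covariate. If baseline is missing, both are undefined at every visit. The missing-at-random property relied on in section 3.4.2 covers missing follow-up scores of a patient who is in the model. It does not bring in a patient with no covariate value.

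**The case against.** The strongest counter-argument is that the decisive fact is not in the document. An order of events is not a time of disclosure: an allocation can be made in REDCap and told to the patient only after the baseline questionnaire. Chapter 2 presents itself as a summary, and the protocol, not shown here, may settle the matter. This stands. A reader might infer that the primary comparison is biased, or that randomisation no longer protects it. The SAP does not support that, because it never says patients knew their arm at baseline.

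Three other readings also go too far:

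- That the trial's error rate rises to 10 to 20%. That is the ungated contrast; the planned gate brings it to about 6 to 13% under the same assumed shift.
- That subtracting baseline and adjusting for it are two separate sources of bias. Algebraically they are one.
- That the PHQ-15 < 10 criterion distorts the primary result. Section 5.3.5 uses the per-protocol set only for a sensitivity analysis, and the full analysis set is not restricted by this criterion.

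Some protection is already planned. Section 3.4.1 tabulates missing baseline values by arm and section 5.1.1 summarises baseline PHQ-15 by arm, so a large shift might be noticed. But a chance imbalance and an allocation-induced one look alike in that table unless it is set against the screening score. The multiple imputation in sections 3.4.2 and 5.3.5 is conditional on more than 5% missing outcomes, and neither section says that a missing baseline would be imputed.

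**Conclusion.** The concern holds in a conditional form. That baseline follows randomisation is stated, not inferred, and no patient blinding is claimed. If patients knew their arm before the baseline PHQ-15, the adjusted effect moves by about 0.10 to 0.14 SD for a 0.2 SD shift and slopes of 0.5 to 0.7, in an unknown direction. The gated false-positive rate is then about 6 to 13% instead of about 2.5%. If allocation was disclosed only afterwards, and treatment had not begun, this bias is zero. Slope and shift are assumptions, and the gated rates come from a single-visit simplification of the mixed model.

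Two parts hold regardless of disclosure: randomised patients without a baseline questionnaire leave the primary model, and the per-protocol set selects on a post-randomisation value. The SAP gives no count for either, so their size cannot be estimated here.

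**What to change.** Keep the change-from-baseline model as primary; replacing it would redefine the endpoint in a finalised plan. Then:

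1. In section 5.3.5, prespecify a key sensitivity analysis with PHQ-15 at each visit as outcome and the pre-randomisation screening PHQ-15 as covariate, other terms as in section 5.3.1. Include randomised patients who lack a baseline questionnaire but have a follow-up score. State how those with neither are reported.
2. In section 3.2, delete the criterion based on baseline PHQ-15 below 10. The screening threshold is already covered by the item on violated inclusion and exclusion criteria.
3. In section 5.1.1, tabulate the change from screening to baseline PHQ-15 by arm. Some fall is expected in every arm because patients were selected at 10 or above; the difference between arms is what matters.
4. In section 2.2, state when patients learned their allocation relative to the baseline questionnaire.

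The cost is some wording, one table and one extra model, assuming the screening score was stored as a number and not only as a pass or fail. The screening score is truncated at 10, so it may predict follow-up slightly less well and the sensitivity estimate may be a little less precise. The sample size is unaffected.

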2.3 Sample Size

The trial is powered for the comparison between the COV.EXPECT group and the TAU group. The type one error (alpha) is not adjusted for multiplicity due to the closed testing principle. A between-group effect size of d=0.5 is expected between COV.EXPECT and TAU for the change from baseline in the PHQ-15 score at 3 months. To detect this effect with a power of 80% and using a two-sided alpha of 5%, 64 patients in each group will be required, resulting in a total sample size of N=192. Assuming a loss to follow-up between baseline and 3 months (time point for primary outcome) of 25%, this results in N=258 randomised patients. Assuming that 50% of the screened patients meet the inclusion criteria, a total of N=516 patients will be assessed for eligibility.

2.4 Statistical Interim Analyses and Stopping Guidance

No interim analysis and stopping guidance is planned.

2.5 Timing of Analyses

Information on the outcomes are collected at baseline, 6 weeks (intermediate), 3 months (post-interventional), and 6 months (follow-up) after baseline.

The analysis will be conducted at two time points. First it will be conducted after all 3-month follow-up visits are conduced (3 months after randomisation of last patient) and after the database has been reviewed for completeness and accuracy. A soft database lock will be conducted.

The final statistical analysis of the study on all primary and secondary endpoints will be conducted after final database lock and data cleaning at the end of study, i.e. when all data from all subjects have been collected, checked for quality and released for analysis. This is scheduled at about 2 years after recruitment of the first patient.

Version 1.0 Page 9 of 18

3 Statistical Principles

In this chapter, the basic statistical principles for the analyses are summarised.

3.1 Confidence Intervals and P Values

For the primary analysis, the significance level is α =0.05 (two-sided). All further analyses are exploratory and will not be adjusted for multiplicity. All applicable statistical tests will be two-sided. All reported confidence intervals (CI) are at 95% level and two-sided.

3.2 Adherence and Protocol Deviations

Both experimental arms (COV.EXPECT, COV.SUPPORT) receive three individual online video consultation sessions with an interval of 2 weeks with given homework after each session and a booster session after 3 months, each lasting 45 minutes. The adherence to the intervention is evaluated based on the number and duration of attended online sessions.

Major protocol deviations will lead to exclusion of a subject from the Per Protocol Population (see Section 3.3.2). Major protocol deviations are any unapproved changes in the research study design and/or procedures that are within the investigator's control and not in accordance with the independent ethics committee (IEC) / institutional review board (IRB) - approved protocol that may affect the subject's rights, safety or well-being, or the completeness, accuracy and reliability of the study data.

Protocol deviations (PD) are defined as follows:

Major PDs:

- Violation of in- and exclusion criteria
- PHQ-15 < 10 in the baseline assessment (in deviation from the inclusion screening)
- At 3-month follow-up:
 - More than 1 missing intervention session (COV.EXPECT, COV.SUPPORT)
 - More than 1 substantially shortened intervention session (< 30 minutes session time)

Additionally, there will be a blind review of a list of further detected protocol violations. The principal investigator will decide which reported protocol violations are considered major and potentially impact the study results.

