3.3.2 Per Protocol Population (PP)

The Per Protocol population (PP) is a subset of the FAS and includes only patients who have no major protocol violation. Patients are analyzed as belonging to the randomised treatment group.

Version 1.0 Page 10 of 18

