5.3.5 Sensitivity Analyses

The primary analysis (mixed linear model based on implicit MAR assumptions) will be repeated in the PP set. Furthermore, for the primary analysis a multiple imputation procedure will be conducted in case more than 5% of values are missing for the primary outcome.

Also, a potential effect of recruitment setting will be investigated by including setting as a fixed effect in the primary analysis model.

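### Attendance-based per-protocol exclusions can fall only on the two active arms, so the PP contrast with TAU is open to selection bias of unknown direction and should not be read as confirming the primary result

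*SAP*

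**What the plan says.** SAP section 3.2 lists four major deviations. Two can occur in any arm: "Violation of in- and exclusion criteria" and "PHQ-15 < 10 in the baseline assessment (in deviation from the inclusion screening"). Two concern exposure up to the 3-month follow-up: "More than 1 missing intervention session (COV.EXPECT, COV.SUPPORT") and "More than 1 substantially shortened intervention session (< 30 minutes session time"). The second exposure line does not name the arms, but section 2.1 gives the control group TAU only, so a TAU patient cannot meet either criterion. Further exclusions may come from case review in any arm: "Additionally, there will be a blind review of a list of further detected protocol violations".

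Section 3.3.2 defines the PP set as a subset of the FAS that "includes only patients who have no major protocol violation", analysed as randomised. Section 5.3.5 gives its use: "The primary analysis (mixed linear model based on implicit MAR assumptions) will be repeated in the PP set". That model (section 5.3.1) adjusts for gender and baseline PHQ-15 and tests COV.EXPECT and COV.SUPPORT each against TAU. The data for another approach are recorded: "The adherence to the intervention is evaluated based on the number and duration of attended online sessions" (section 3.2).

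The primary analysis is on the FAS (section 3.3.1), and section 3.1 calls everything beyond the primary analysis exploratory.

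**The concern.** Attendance is decided after randomisation and may be linked to prognosis. Sessions last 45 minutes and carry homework. Fatigue and post-exertional malaise, which could affect attendance, are endpoints of the trial but not covariates in the model. If poor attenders differ in prognosis, the rule changes the case mix of each active arm and leaves that of TAU as it was.

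The MAR assumption of the mixed model does not repair this. An excluded patient's observed 6-week and 3-month scores are removed from the analysis; they are not treated as missing values to be modelled.

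The PP repeat is the only planned efficacy analysis that uses attendance. A PP effect larger than the FAS effect would invite the reading that patients who attend benefit more, when selection alone could produce the same pattern. The SAP says nothing about how such a difference is to be interpreted.

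**Working it through.** **1. The plan's own figures (section 2.3).** With d=0.5, two-sided alpha 5% and 80% power, the two-sample t-test needs 63.77, so 64 per group; power at 64 is 0.801. With 25% loss, 64/0.75 rounds up to 86 per arm, and 3 × 86 = 258. The stated sample size reproduces. The SAP gives no figure for PP exclusions, so the inputs below are assumptions.

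**2. Which rules reach which arm**

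| Major deviation (section 3.2) | COV.EXPECT, COV.SUPPORT | TAU |
|---|---|---|
| Eligibility violation | yes | yes |
| Baseline PHQ-15 below 10 | yes | yes |
| Added at blind review | yes | yes |
| More than one missed session | yes | not possible |
| More than one session under 30 minutes | yes | not possible |

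**3. Bias when the intervention does nothing.** Let p be the share of an active arm excluded for low exposure, and r the correlation of attendance propensity with PHQ-15 improvement after adjustment. With a normal propensity cut at its p-quantile z_p, the retained patients' mean is shifted by r × φ(z_p)/(1−p). The multiplier φ(z_p)/(1−p) is 0.195, 0.350 and 0.497 for p = 10%, 20% and 30%.

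| p | r=0.1 | r=0.2 | r=0.3 |
|---|---|---|---|
| 10% | 0.02 SD | 0.04 SD | 0.06 SD |
| 20% | 0.03 SD | 0.07 SD | 0.11 SD |
| 30% | 0.05 SD | 0.10 SD | 0.15 SD |

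Against d=0.5 this is 4% (0.02/0.5) to 30% (0.15/0.5).

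**4. Second parametrisation.** If a share f is excluded and attenders improve D SD more than non-attenders, the bias is f × D. For f=0.2 and D=0.5 it is 0.10 SD. The attenders' variance is 1 − 0.2×0.8×0.25 = 0.96, and the standard error is √(0.96/51.2 + 1/64) = 0.185. A nominal 5% pairwise test then rejects in 8.4% of null trials. For f=0.3 and D=0.5 the figures are 0.15 SD and 12.2%. For D=0 they are 0 and 5.0%. For D=−0.3 the bias is −0.03 to −0.09 SD over f = 10-30%, against the intervention.

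**5. Effect of the testing sequence.** Section 5.3.1 tests contrasts only after a significant global F-test. Simulated null trials with 64 per arm before exclusion gave these rejection rates:

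| p, r | Pairwise test, no gate | Global F-test | COV.EXPECT vs TAU after the gate |
|---|---|---|---|
| 20%, 0.2 | 6.9% | 6.5% | 3.6% |
| 20%, 0.3 | 8.5% | 8.5% | 5.1% |
| 30%, 0.3 | 11.8% | 11.6% | 7.3% |

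The ungated rates therefore overstate false positives for the planned contrast procedure, although the F-test itself is inflated. The bias in the point estimate and interval (step 3) does not depend on the gate.

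**The case against.** The strongest reply is that little hangs on this. The primary analysis keeps all randomised patients, the PP repeat carries no alpha and no decision rule, and excluding under-exposed patients is a conventional, pre-specified choice. All of that stands, and it limits the point to a cheap improvement. But calling an analysis exploratory does not tell the reader that it is not a randomised comparison.

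The inputs are also open to challenge. With three sessions before the booster, exclusion for absence needs at least two missed, and non-attenders may overlap with the 25% already assumed lost, so p could be small. At p=10% and r=0.1 the bias is only 0.02 SD. This stands too.

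A reader might infer that the PP analysis must favour the interventions even if they do nothing. The document does not support that: it says nothing on the prognosis of non-attenders, and patients who stop because they have improved would push the bias the other way. Nor does the PP set compare attenders with every TAU patient, since TAU patients also leave it for eligibility, low baseline PHQ-15 or blind-review findings.

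On the remedy, an instrumental-variable test of no effect largely reproduces the intention-to-treat test, so its null estimate near zero is expected by construction. It adds an estimate of the effect in those who attend, not independent evidence. It also answers a different question from the PP analysis.

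**Conclusion.** The asymmetry is certain from the text: the two exposure criteria act only in the active arms, after randomisation, and nothing in the PP analysis corrects for it. The PP contrasts with TAU are unbiased under the null only if attendance is unrelated to prognosis given gender and baseline PHQ-15, an assumption the SAP does not state.

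The consequence is possible rather than demonstrated. Bias towards the interventions is plausible, at about 0.02-0.15 SD under the assumed exclusion of 10-30% and correlation of 0.1-0.3, but neither sign nor size can be read from the SAP. The FAS primary analysis and its error rate are untouched. This is a cheap improvement to a sensitivity analysis, not a flaw in the trial's main claim.

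**What to change.** In section 5.3.5:

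- Keep the PP analysis. State that its contrasts with TAU are non-randomised and selection-prone and do not confirm the primary result. Report PP exclusions by arm and reason.
- Add, in the FAS and separately for each active arm against TAU, a complier-average causal effect on the 3-month change in PHQ-15. Use randomised arm as the instrument, baseline PHQ-15 and gender as covariates, and a binary exposure: meeting the SAP's own attendance and duration criteria by 3 months. As long as TAU patients cannot obtain the sessions, non-adherence is one-sided, and the unadjusted estimate is the FAS difference divided by the share of the active arm that meets the criteria.
- If the number of sessions is used as exposure instead, label the result a per-session effect under linearity, not a complier-average effect.
- State how missing 3-month scores are handled in this model, since it does not inherit the mixed model's treatment of them.

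The cost is SAP wording and one further model per active arm, on data already recorded. The estimate rests on the exclusion restriction: allocation acts only through the exposure, which with a binary exposure also means no effect of partial attendance. Its interval is wider. Relative to the FAS contrast the standard error grows by roughly 1/(1−p), so at p=20% by 1/0.8 = 1.25. With 64 per arm that is √(2/64)/0.8 = 0.22 SD, against √(1/64 + 1/51.2) = 0.19 SD for the PP contrast.
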